6.3.1.3.2 Follow up on potential drug-induced liver injury (DILI) cases

Patients with transaminase increase combined with total bilirubin (TBIL) increase may be indicative of drug-induced liver injury (DILI), and should be considered as clinically important events.

The threshold for potential DILI may depend on the patient's baseline AST/ALT and TBIL value; patients meeting any of the following criteria will require further follow-up as outlined below:

- For patients with normal ALT and AST and TBIL value at baseline: AST or ALT > 3.0 x ULN combined with TBIL > 2.0 x ULN
- For patients with elevated AST or ALT or TBIL value at baseline: [AST or ALT > 2 x baseline AND > 3.0 x ULN] OR [AST or ALT > 8.0 x ULN], , combined with [TBIL > 2 x baseline AND > 2.0 x ULN]

Medical review needs to ensure that liver test elevations are not caused by cholestasis, defined as: Alkaline Phosphatase (ALP) elevation $> 2.0 \times ULN$ with R value < 2 in patients without bone metastasis, or elevation of ALP liver fraction in patients with bone metastasis.

Note: The R value is calculated by dividing the ALT by the ALP, using multiples of the ULN for both values. It denotes the relative pattern of ALT and/or ALP elevation is due to cholestatic ($R \le 2$), hepatocellular ($R \ge 5$), or mixed (R > 2 and < 5) liver injury.

In the absence of cholestasis, these patients should be immediately discontinued from study drug treatment, and repeat Liver Function Tests as soon as possible, preferably within 48 hours from the awareness of the abnormal results. The evaluation should include laboratory tests, detailed history, physical assessment and the possibility of liver metastasis or new liver lesions, obstructions/compressions, etc.

Hepatic toxicity monitoring includes the following LFTs: albumin, ALT, AST, total bilirubin, direct and indirect bilirubin, alkaline phosphatase (fractionated if alkaline phosphatase is grade 2 or higher), creatine kinase, prothrombin time (PT) or INR and GGT. For patients with Gilbert's Syndrome: total and direct bilirubin must be monitored, intensified monitoring applies to changes in direct bilirubin only.

Close observation is recommended in case of AST, ALT, and/or bilirubin increase requiring dose interruption, which involves:

- Repeating liver enzyme and serum bilirubin tests **two or three times weekly**. Frequency of re-testing can decrease to once a week or less if abnormalities stabilize or return to normal values.
- Obtaining a more detailed history of current symptoms.
- Obtaining a more detailed history of prior and/or concurrent diseases, including history of any pre-existing liver conditions or risk factors.
- Obtaining a history of concomitant drug use (including non-prescription medications, herbal and dietary supplements), alcohol use, recreational drug use, and special diets.
- Ruling out acute viral hepatitis types A, B, C, D, and E; hepatotropic virus infections (CMV, EBV or HSV); autoimmune or alcoholic hepatitis; NASH; hypoxic/ischemic hepatopathy; and biliary tract disease.

- Obtaining a history of exposure to environmental chemical agents.
- Obtaining additional tests to evaluate liver function, as appropriate (e.g., INR, direct bilirubin).
- Considering gastroenterology or hepatology consultations.

6.3.1.3.3 Additional follow-up for QTc prolongation

- Assessing cardiovascular dysfunction or impaired liver oxygenation, including hypotension or right heart failure as possible etiologies for liver dysfunction.
- Consider a liver biopsy as clinically indicated to assess pathological change and degree of potential liver injury

All cases of DILI confirmed on repeat testing meeting the laboratory criteria defined above, with no other alternative cause for LFT abnormalities identified, should be considered as "medically significant", thus meeting the definition of SAE (Section 8.2.1), and must be reported as SAE using the term "potential drug-induced liver injury". All events must be followed up with the outcome clearly documented. Results of tests as well as other clinically important information will be recorded in the eCRF.

Grade	Dose Modification	
For All Grades	1. Check the quality of the ECG and the QT value and repeat if needed.	
	 Perform analysis of serum electrolytes (K+, Ca++ correct for albumin, Phos, Mg++). If outside of the normal range, interrupt ribociclib administration, correct with supplements or appropriate therapy as soon as possible, and repeat electrolytes until documented as normal. 	
	 Review concomitant medication usage for the potential to inhibit CYP3A4 and/or to prolong the QT interval. 	
	4. Check compliance with correct dose and administration of ribociclib.	
1 QTcF 450-480 ms	Perform steps 1-4 as directed in "For All Grades." No dose adjustment required.	
2	Interrupt ribociclib. Perform steps 1-4 as directed in "For All Grades."	
QTcF 481-500 ms	Perform a repeat ECG within one hour of the first QTcF of \geq 481 ms.	
	Repeat ECG as clinically indicated until the QTcF returns to < 481 ms. Restart ribociclib with dose reduced by 1 dose level. Refer to Table 6-2 for dosing schedule.	
	If QTcF \ge 481 ms recurs, ribociclib should be reduced again by 1 dose level.	
	Repeat ECG 7 days and 14 days after dose resumption (then as clinically indicated) for any patients who had therapy interrupted due to $QTcF \ge 481$ ms	
3	Interrupt ribociclib. Perform steps 1-4 as directed in "For All Grades."	
QTcF ≥ 501 ms on at least	Perform a repeat ECG within one hour of the first QTcF of \geq 501 ms.	
two separate ECGs	If QTcF remains \ge 501 ms, consult with a cardiologist (or qualified specialist) and repeat cardiac monitoring as indicated until the QTcF returns to < 481 ms.	
	 If QTcF returns to < 481 ms, ribociclib will be reduced by 1 dose level. Refer to Table 6-2 for dosing schedule. 	
	• If QTcF remains ≥ 481 ms after performing steps 1-4 as directed in "For All Grades," discontinue ribociclib.	
	Repeat ECG 7 days and 14 days after dose resumption (then as clinically indicated) for any patients who had therapy interrupted due to $QTcF \ge 501$ ms If $QTcF$ of ≥ 501 ms recurs, discontinue ribociclib.	

Table 6-5 Ribociclib dose adjustment and management recommendation for QTcF prolongation

Grade	Dose Modification
4 [QT/QTcF ≥ 501 or > 60 ms change from baseline] and [Torsades de pointes or polymorphic ventricular tachycardia, or signs/symptoms of serious arrhythmia]	 Discontinue ribociclib. Perform steps 1-4 as directed in "For All Grades." Obtain local cardiologist (or qualified specialist) consultation and repeat cardiac monitoring as indicated until the QTcF returns to <481 ms.

6.3.1.3.4 Additional follow-up for Interstitial Lung Disease (ILD)/pneumonitis (CTCAE v4.03)

Table 6-6 Ribociclib dose adjustment and management recommendation for ILD/pneumonitis

Grade	Dose Adjustment and Management Recommendations
1 (asymptomatic)	No dose adjustment required. Initiate appropriate medical therapy and monitor as clinically indicated.
2 (symptomatic)	Interrupt ribociclib dose until recovery to Grade ≤1, then resume ribociclib at the next lower dose level*.
3 and 4 (severe)	Discontinue ribociclib

* An individualized benefit-risk assessment should be performed before resuming ribociclib

6.3.1.3.5 Guidance for all other adverse reactions

Consider performing an analysis of serum potassium, calcium, and magnesium for all adverse reactions that are potentially associated with electrolyte imbalance. If electrolyte values are outside of the normal range, interrupt ribociclib administration, correct electrolytes with supplements or appropriate therapy as soon as possible, and repeat electrolyte testing until documented normalization of the electrolytes.

For all other adverse events, including Toxic Epidermal Necrolysis (TEN), which is a grade-4 event by CTCAE, please follow recommendations in Table 6-7.

Table 6-7Ribociclib dose reduction/interruption and managementrecommendation for all other adverse reactions

Grade	Dose Adjustment and Management Recommendations
1	No dose adjustment recommended. Initiate appropriate medical therapy and monitor.
2	Dose interruption until recovery to grade ≤ 1 . Initiate appropriate medical therapy and monitor. Re-initiate ribociclib at the same dose. If the same toxicity recurs at grade 2, interrupt ribociclib until recovery to grade ≤ 1 . Re-initiate ribociclib at the next lower dose level.

Novartis	Confidential	Page 65
Amended Protocol Version 04 (Clean)		Protocol No. CLEE011A2404

3	Dose interruption until recovery to grade ≤1. Initiate appropriate medical therapy and monitor. Re-initiate ribociclib at the next lower dose level. If toxicity recurs at grade 2: temporary dose interruption until recovery to grade ≤1 and reduce ribociclib dose the next lower dose level. If toxicity recurs at grade 3, discontinue ribociclib.
4	Discontinue ribociclib and treat with appropriate medical therapy.

6.3.2 Follow-up for toxicities

Patients who complete treatment or whose treatment is interrupted or permanently discontinued due to an adverse event or clinically significant laboratory value, must be followed at least once a week (or more frequently if required by institutional practices, or if clinically indicated) for 4 weeks, and subsequently at approximately 4-week intervals, until resolution or stabilization of the event, whichever comes first. Appropriate clinical experts such as ophthalmologist, endocrinologist, dermatologist, psychiatrists etc. should be consulted as deemed necessary.

All patients will be followed up for adverse events and serious adverse events for 30 days following the last dose of study treatment. Patients stopping study treatment but still receiving ribociclib outside of this trial (e.g., commercial supply) will be followed up for safety up to 30 days independently of resolution/stabilization of AEs. Further reports of AEs after 30 days of EOT should follow local pharmacovigilance practices.

6.4 Concomitant medications

6.4.1 Permitted concomitant therapy

Medications required to treat AEs, manage cancer symptoms, concurrent diseases and supportive care agents, such as pain medications, anti-emetics and anti-diarrheals are allowed. Please consult the list of prohibited medications and the list of use with caution medications for further guidance (see Table 14-1 and Table 14-2 in Appendix 14.1).

The patient must be told to notify the investigational site about any new medications he/she takes after the start of the study drug. All medications (other than study drug) and significant non-drug therapies (including physical therapy, herbal/natural medications and blood transfusions) administered during the study must be listed on the Prior and Concomitant Medications or the Surgical and Medical Procedures eCRF.

If patients take concomitant medications chronically, any change in the dose or schedule of any concomitant medication throughout the study period should be clearly documented

6.4.1.1 Bisphosphonates and denosumab

Bisphosphonates and denosumab are generally allowed with the following comments:

- Bisphosphonate/denosumab therapy for the treatment of osteoporosis is permitted.
- Bisphosphonate/denosumab therapy for the prevention of skeletal related events for patients with bone metastases is permitted.
- Chronic concomitant bisphosphonate/denosumab therapy for **the prevention of bone metastasis** is permitted.

Patients taking concomitant medication chronically should be maintained on the same dose and dose schedule throughout the study period, as medically feasible.

6.4.1.2 Hematopoietic growth factors

Prophylactic use of WBC growth factors with ribociclib is not recommended.

6.4.1.3 Palliative radiotherapy

Palliative radiation is permitted. It should not be delivered to target lesion. Cumulative courses of RT should not encompass >25% of irradiated bone marrow (see Appendix 14.4).

If palliative radiotherapy is initiated after the start of study treatment, the reason for its use must be clearly documented and progression must be ruled out.

No dose modification of study treatment is needed during palliative radiotherapy.

6.4.1.4 Use of antiemetic medications

Ribociclib has low to minimal emetogenic potential according to the definition of antineoplastic agent emetogenicity (Grunberg et al 2010). Antiemetic therapy can be used according to clinical guidelines for antineoplastic medications with low to minimal emetogenic potential for treatment and/or prevention of nausea and vomiting as a result of study treatment (NCCN Clinical Practice Guidelines in Oncology. Antiemesis, 2017; Roila F et al 2016).

Potential drug interaction between ribociclib and antiemetic medications should always be taken into consideration. Example of a prohibited antiemetic medication is ondansetron that in combination with ribociclib may precipitate TdP. Refer to Appendix 1 for list of medications that are prohibited or allowed to be used with ribociclib.

6.4.2 Permitted concomitant therapy requiring caution

Medications to be used with caution during combined ribociclib and letrozole (+/- goserelin or leuprolide) in this study are listed below (see Table 14-2 in Appendix 14.1). This list is not comprehensive and is only meant to be used as a guide. Please contact the medical monitor with any questions. These medications should be excluded from patient use if possible. If they must be given based on the investigator's judgment, then use with caution and consider a ribociclib interruption if the concomitant medication is only needed for a short time.

- Moderate inhibitors or inducers of CYP3A4/5 (may increase or decrease ribociclib exposure, respectively)
- Sensitive substrates of CYP3A4/5 that do not have narrow therapeutic index (ribociclib may increase exposure to these medications)
- Strong inhibitors of BSEP (Bile Salt Export Pump) (based on *in vitro* data coadministration with ribociclib may lead to intrahepatic cholestasis)
- Medications that carry a possible risk for QT prolongation (may precipitate QT prolongation and TdP)
- Sensitive substrates of the renal transporters, MATE1 and OCT2 (has a potential to increase exposure to substrates of these transporters, although no animal or clinical data are available to support these statements)

- Sensitive substrates of transporter BCRP (has a potential to increase exposure to substrates of these transporters, although no animal or clinical data are available to support these statements)
- Substrates metabolized predominantly by CYP2C19 or CYP2A6 with a narrow therapeutic index (that could be affected by letrozole)

6.4.2.1 Corticosteroids

Chronic dosing of corticosteroids such as dexamethasone and prednisone is known to lead to induction of CYP3A enzymes, thereby potentially reducing ribociclib drug exposure to subtherapeutic levels. Systemic corticosteroid treatment should not be given during the study, except for:

- Topical applications (e.g., for rash), inhaled sprays (e.g., for obstructive airways diseases), eye drops or local injections (e.g., intra-articular);
- A short duration (< 5 days) of systemic corticosteroids ≤ to the anti-inflammatory potency of 4 mg dexamethasone (e.g. for chronic obstructive pulmonary disease, or as an antiemetic)

6.4.3 Prohibited concomitant therapy

The following medications are prohibited during study treatment in the study (see Table 14-1 in Appendix 14.1). This list is not comprehensive and is only meant to be used as a guide. Please contact the medical monitor with any questions:

- Strong inhibitors or inducers of CYP3A4/5 (may significantly increase or decrease ribociclib exposure, respectively)
- Substrates of CYP3A4/5 with a narrow therapeutic index (ribociclib may increase exposure to these medications resulting in toxicity to these medications)
- Medications with a known risk for QT prolongation (may precipitate QT prolongation and TdP in combination with ribociclib)
- Other investigational and antineoplastic therapies
- Herbal preparations/medications or dietary supplements that are strong inhibitors or inducers of CYP3A4/5 or those with a known risk of QT prolongation. These include but are not limited to: St. John's wort, Kava, ephedra (ma huang), gingko biloba, dehydroepiandrosterone (DHEA), yohimbe, saw palmetto, black cohosh and ginseng. Patients should stop using all these preparations at least 7 days prior to first dose of study treatment.

6.4.4 Drugs with QT prolongation

As far as possible, avoid co-administering medications with a "Known", "Possible" or "Conditional" risk of TdP (www.crediblemeds.org) or any other medication with the potential to increase the risk of drug-related QT prolongation (e.g. via a potential DDI increasing the exposure of ribociclib or the exposure of the QT prolonging drug). If concomitant administration of drugs with a known risk of TdP is required and cannot be avoided, ribociclib must be interrupted (see Table 6-5). If during the course of the study, concomitant administration of a drug with "Possible risk" or "Conditional risk" of TdP is required, based on

the investigator assessment and clinical need, study treatment may be resumed under close clinical and ECG monitoring to ensure patient safety. A list of drugs associated with QT prolongation and/or TdP is available online (www.crediblemeds.org). Medications with a known risk for QT prolongation are prohibited during study treatment.

Confidential

Refer to the ribociclib [Investigator's Brochure] and letrozole, goserelin, and leuprolide drug package insert in addition to Appendix 14.1 for information on possible interactions with other drugs.

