Study treatment discontinuation	Point/time when patient permanently stops taking study treatment for any reason.
Subject Number	A unique identifying number assigned to each patient/subject/healthy volunteer who enrolls in the study
Supportive treatment	Refers to any treatment required by the exposure to a study treatment, e.g. premedication of vitamin supplementation and corticosteroid for pemetrexed disodium.

Glossary of terms

Confidential

Treatment group	A treatment group defines the dose and regimen or the combination, and may consist of 1 or more cohorts. Cohorts are not expanded, new cohorts are enrolled.			
Variable	Identifier used in the data analysis; derived directly or indirectly from data collected using specified assessments at specified timepoints			
Withdrawal of Consent	Jrawal of Consent Withdrawal of consent occurs only when a patient does not want to particip the study any longer, and does not want any further visits or assessments, does not want any further study related contact			

Protocol summary

Title	An open-label, multicenter, Phase IIIb study to assess the safety and efficacy of ribociclib (LEE011) in combination with letrozole for the treatment of men and pre/postmenopausal women with hormone receptor-positive (HR+) HER2-negative (HER2-) advanced breast cancer (aBC) with no prior hormonal therapy for advanced disease		
Brief title	Study to assess the safety and efficacy of ribociclib (LEE011) in combination with letrozole for the treatment of men and pre/postmenopausal women with HR+ HER2- aBC in a broader population		
Sponsor and Clinical Phase	Novartis Phase IIIb		
Investigation type	Drug		
Study type	Interventional		
Purpose and rationale	The purpose of this Phase IIIb study is to collect additional safety and efficacy data for the combination of ribociclib + letrozole in a broader population of patients with HR+HER2- aBC in comparison with other Phase III studies with ribociclib.		
Primary Objective(s) and Key Secondary Objective	To evaluate the safety and tolerability of ribociclib with letrozole in men and pre/postmenopausal women with HR+, HER2- aBC who received no prior hormonal therapy for advanced disease Note: Throughout this document, perimenopausal and premenopausal status will be grouped together and referred as "Premenopausal"		

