6.1 Study treatment

For this protocol, the term "investigational drug" refers to the Novartis study drug ribociclib. The other drugs to be used in this study are letrozole and either goserelin or leuprolide (for men / premenopausal women). "Study treatment" in this protocol refers to the combination of drugs and includes investigational drug (ribociclib) as well as letrozole and goserelin or leuprolide (if applicable).

Ribociclib will be supplied by Novartis or its designee as 200 mg tablets as individual patient supply packaged bottles. Letrozole (Femara or generic equivalent), goserelin and leuprolide will be procured locally by Country Pharma Organization or local institution as it is commercially available in each participating country according to local practices and regulations. Storage conditions are described in the medication label. Medication labels will comply with the legal requirements of each country and be printed in the local language.

All dosages prescribed and dispensed to the patient and all dose changes during the study must be recorded on the Dosage Administration Record in the eCRF.

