6.3 Dose modifications

6.3.1 Dose modification and dose delay

For patients who do not tolerate the protocol-specified dosing schedule, dose interruptions and/or reductions are either recommended or mandated in order to allow patients to continue the study treatment. These dose modifications are summarized in Table 6-2, Table 6-3, Table 6-4, Table 6-5, Table 6-6, and Table 6-7. No dose re-escalation is permitted.

Clinical judgment of the treating physician should guide the management plan of each patient based on individual benefit/risk assessment. However, for events requiring a discontinuation in Table 6-3, Table 6-4, Table 6-5, Table 6-6, and Table 6-7 or listed in Section 7.1.5., treatment must be discontinued. If dosing was interrupted for >28 days due to ribociclib related toxicity, ribociclib must be discontinued.

Novartis	Confidential	Page 58
Amended Protocol Version 04 (Clean)		Protocol No. CLEE011A2404

Dose reductions are not permitted for letrozole, goserelin or leuprolide.

Any changes to ribociclib dose or interruption of the study treatment must be recorded on the Dosage Administration Record eCRF. All patients will be followed for (S)AEs for 30 days following the last dose of ribociclib.

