7.1.5 Discontinuation of study treatment

Patients may voluntarily discontinue from the study treatment for any reason at any time.

If a patient decides to discontinue from the study treatment (Core or Extension Phase), the investigator must make a reasonable effort (e.g. telephone, e-mail, letter) to understand the primary reason for this decision and record this information in the patient's chart and on the appropriate eCRF pages. They may be considered withdrawn if they state an intention to withdraw, fail to return for visits, or become lost to follow-up for any other reason.

- The investigator may discontinue study treatment (Core or Extension Phase) for a given patient if, on balance, he/she believes that continuation would be detrimental to the patient's well-being.
- Patients will discontinue from the Core Phase 18 months after LPFV. In the event study patients are still deriving benefit at the end of the Core Phase and ribociclib is not approved or available and reimbursed, patients may be transitioned to the Extension Phase and continue to receive the study treatment until progression, intolerance, death, or physician/patient decision; only safety and clinical benefit as assessed by investigator will be collected.
- During the Extension Phase, if ribociclib is approved and reimbursed, patients will be transitioned to prescription or drug access/support program(s) according to local laws and regulations.
- The study will end after completion of the Extension Phase and all remaining patients will discontinue from the study. Patients who complete this Extension Phase, and continue to derive clinical benefit from the treatment based on the investigator's evaluation will

receive ribociclib from prescription (if approved and reimbursed), another Post-Trial Access (PTA) program, or other drug access/support program(s).

Patients may voluntarily withdraw from the study or be dropped from it at the discretion of the investigator at any time.

Patients may be withdrawn from the study treatment if any of the following occur:

- Adverse Event
- Lost to follow-up
- Physician decision
- Progressive Disease
- Protocol deviation
- Study terminated by sponsor
- Technical problems

Patients must be withdrawn from the study treatment if any of the following occur:

- Pregnancy
- Death
- Subject/Guardian decision

In addition to the general withdrawal criteria, the following study specific criteria will also require study treatment discontinuation:

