- Adjustments to study treatment due to toxicity that result in discontinuation. Please refer to Section 6.3
- Use of prohibited medication. Please refer to Section 6.4.3
- Any other protocol deviation that results in a significant risk to the patient's safety.

Patients who discontinue study treatment should undergo an End of Treatment (EOT) visit followed by a 30-day safety follow-up.

At EOT visit, all the assessments as listed in Table 7-1 will be performed. If the decision to discontinue the patient occurs at a regularly scheduled visit, that visit may serve as the EOT visit rather than having the patient return for an additional visit.

The investigator or his/her delegate must also contact the IRT to register the patient's discontinuation from study treatment within 2 days of EOT visit.

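### Protocol 6.4.4 interrupts ribociclib for an unavoidable drug with known TdP risk, while 6.4.3 with 7.1.5 and 6.3.1 requires permanent discontinuation of study treatment for the same use

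*Protocol*

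**What the plan says.** Protocol 6.4.4 foresees that a drug with known TdP risk may be needed and states the consequence: "If concomitant administration of drugs with a known risk of TdP is required and cannot be avoided, ribociclib must be interrupted". It refers to Table 6-5 for this. Later in the same section it states: "Medications with a known risk for QT prolongation are prohibited during study treatment".

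Protocol 6.4.3 has the class on its prohibited list: "Medications with a known risk for QT prolongation (may precipitate QT prolongation and TdP in combination with ribociclib"). It makes no exception for use that cannot be avoided.

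Protocol 7.1.5 first gives reasons for which a patient may be withdrawn from treatment. It then gives a mandatory list, saying that "the following study specific criteria will also require study treatment discontinuation", and one item on that list is "Use of prohibited medication. Please refer to Section 6.4.3". Protocol 6.3.1 leaves management to the treating physician in general but excepts certain events, including those "or listed in Section 7.1.5., treatment must be discontinued".

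Two definitions matter. The glossary defines study treatment discontinuation as: "Point/time when patient permanently stops taking study treatment for any reason". Protocol 6.1 says that study treatment "refers to the combination of drugs and includes investigational drug (ribociclib) as well as letrozole and goserelin or leuprolide (if applicable").

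SAP 2.4.2.3 expects that some patients will take prohibited drugs, tabulates and lists that use, and records it as a protocol deviation. It does not connect it with discontinuation.

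**The concern.** One event, the unavoidable use of a known-risk drug, carries two mandatory instructions that cannot both be followed. One is a hold of a single drug. The other is a permanent stop of the whole combination. A site that reads 6.4.4 and a site that reads 7.1.5 will act differently on identical patients, and each will be following the protocol.

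For the patient, what is at stake is whether study treatment is lost for good. For the analysis, the same clinical situation can be recorded as an interruption at one site and as a discontinuation at another, so differences in the tables would partly reflect which section was read.

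The situation is foreseeable. Table 14-1 lists azithromycin, ciprofloxacin, levofloxacin, fluconazole and ondansetron as known-risk drugs. Protocol 1.2.1.2.1 reports infections in 50.3% and nausea in 51.5% of the ribociclib arm of the earlier phase III trial.

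**Working it through.** The plan states no figure on this point. The check is a comparison of the text.

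**1. The two rules side by side**

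| | Protocol 6.4.4 | Protocol 6.4.3 with 7.1.5 and 6.3.1 |
|---|---|---|
| Trigger | Known-risk drug, required and unavoidable | Any use of a drug prohibited in 6.4.3 |
| Force | Mandatory | Mandatory; excepted from physician judgment |
| What stops | Ribociclib | Study treatment, i.e. all components |
| Ribociclib while the drug is given | Withheld | Withheld |
| Ribociclib afterwards | Interruption, so resumption is implied | Permanently stopped |
| Letrozole and LHRH agonist | Not stopped | Stopped |

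The trigger in the middle column falls wholly within the one on the right. The rules agree on the fourth row and conflict on the last two.

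**2. Does Table 6-5 settle it?** No. Its interruptions are triggered by QTcF values or abnormal electrolytes. On co-medication it asks only for a review of what the patient takes. It gives no hold or restart condition for an unavoidable known-risk drug. The 28-day limit in 6.3.1 does not fill the gap, because it applies to interruptions for ribociclib-related toxicity.

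**3. Does holding ribociclib put the patient outside study treatment, so that the prohibition no longer applies?** Not on the protocol's definition. Section 6.1 counts letrozole and the LHRH agonist as study treatment, and 6.4.4 interrupts ribociclib only.

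**4. Which summaries move?**

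- SAP 2.4.1.5 summarises interruptions and permanent discontinuations separately, with reasons. An interruption counts only if a non-zero dose later resumes, so the two rules lead to different rows.
- SAP 2.3.5 and 2.3.6 tabulate discontinuation and its primary reason. Only 7.1.5 produces an entry there.
- SAP 2.4.1.1 measures exposure to study treatment up to the latest component. It continues to accrue if letrozole continues and ends if everything stops.
- SAP 2.1.3 closes the on-treatment period 30 days after the last dose of any component (in the Core Phase, for patients who do not transition). The AE window therefore also depends on the rule followed.
- SAP 2.5.1 counts AEs leading to discontinuation and AEs leading to dose reduction or interruption. These change only when the known-risk drug is given for an AE and the dosing action is attributed to that AE.

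**5. How many patients?** The documents give no expected frequency of unavoidable known-risk use. The Amendment 04 rationale gives 3,246 treated, the Core Phase complete, and 415 moved to the Extension Phase: 415 / 3,246 = 12.8%. That is the ceiling on patients whom new wording could reach. It is not an estimate of those affected.

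**The case against.** The best counter-argument is that a specific provision governs a general one. Section 6.4.4 is written for QT drugs and 7.1.5 is a general list, so 6.4.4 could be read as a prohibition with a contingency. The protocol also uses the term study treatment loosely. Section 7.2.2.6.1 interrupts study treatment at a QTcF of 481 ms or more, whereas Table 6-5, to which it refers, interrupts ribociclib only. Section 6.4.3 sends questions to the medical monitor, and the SAP takes interruptions and discontinuations from recorded dosing fields, so its definitions are clear.

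Part of this stands. The fault may well be a drafting gap, and what varies is site behaviour, not the SAP's counting rules. But neither 6.4.3 nor 7.1.5 makes an exception for 6.4.4, and 6.3.1 removes discretion for anything listed in 7.1.5. A reader cannot know that the contingency was meant to prevail.

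Three stronger readings are tempting, and the documents do not support them:

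- A reader might infer that one rule lets ribociclib and the known-risk drug be given together. Neither does.
- A reader might take interruption and discontinuation to be primary endpoint categories in themselves. The categories are AEs that lead to those actions.
- A reader might apply an assumed rate to the planned 3,000 patients. No rate is given, the earlier trial's infection and nausea rates do not show unavoidable use of a listed drug, and Core Phase treatment had ended by Amendment 04.

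**Conclusion.** The contradiction is real and lies in the current text. For unavoidable use of a known-risk drug, the protocol both requires an interruption of ribociclib and requires permanent discontinuation of the combination. Its scope is limited to resumption of ribociclib and continuation of the other components.

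The direct effect is on disposition, the dosing-action summaries, exposure duration and the on-treatment window. The effect on the primary AE-action categories is conditional on attribution to an AE. The number of patients cannot be estimated from the documents. New wording can affect at most the 415 who entered the Extension Phase and cannot alter Core Phase data.

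The conclusion rests on the protocol's own definitions of study treatment and of discontinuation, and on the absence of any exception in 6.4.3 or 7.1.5. It takes no view on which clinical rule is right.

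**What to change.** Reconcile Protocol 6.4.3, 6.4.4, 7.1.5 and 6.3.1 so that a single stated consequence applies to unavoidable use of a known-risk drug. The text should make explicit whether that consequence covers ribociclib alone or all components, and whether it is temporary or permanent. Correct the pointer from 6.4.4 to Table 6-5, since that table has no rule for this trigger. Which consequence applies is for the sponsor's clinicians.

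The cost is protocol wording, with the approvals that any amendment needs under Protocol 12.1. Sample size and analysis methods are unchanged, and the SAP's existing dosing fields will record whichever action is specified.
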